### 5.7.4. Analyses of Other Efficacy Variables

The analyses of other efficacy variables will be the same as the primary analysis described in Section 5.7.1 and Section 5.7.2.

## 5.8. Analysis of Safety Data

The summary of safety and tolerability will be performed based on SAF.

The safety analysis will be based on the reported AEs, clinical laboratory evaluations, physical examination, vital signs and 12-lead ECG.

Thresholds for treatment-emergent Potentially Clinically Significant Values (PCSVs) in laboratory variables and vital signs are defined in [Appendix 10.3](#). Treatment-emergent PCSV is any PCSV developed or worsened in severity compared to the baseline during the treatment and follow-up period.

The time interval to detect any event or abnormality is between the first injection of study medication and EOS.

Subgroups are defined by key baseline factors recorded on the CRF and listed to be considered for safety analyses:

- Age group ( $\geq 12$  to  $< 15$ ,  $\geq 15$  to  $< 18$ )
- Sex (Male, Female)
- Ethnicity (Hispanic or Latino (no/yes))
- Race (White, Black, Asian, Other)
- Duration of AD ( $< 13$  years,  $\geq 13$  years)
- Baseline BMI group (overweight:  $\geq 85$  percentile of general population based on age and gender,  $< 85$  percentile)
- Baseline weight group ( $< 60$  kg,  $\geq 60$  kg)

### 5.8.1. Adverse Events

Listings of TEAEs, serious TEAEs, and TEAEs resulting in death and study drug discontinuation will be generated.

Number and proportions of patients reporting TEAEs will be summarized for overall during the study, during the week 16 treatment period and during the follow-up period separately, sorted by decreasing frequency of SOC and PT based on the overall incidence for the combined dupilumab treatment groups.

Summaries of TEAEs will include:

- TEAEs
  - TEAEs by SOC/PT
  - TEAEs by SOC/HLT/PT
  - TEAEs by PT
  - Common TEAEs by SOC/HLT/PT (incidence with PT  $\geq 5\%$ )
  - Common TEAEs by SOC/HLT/PT (incidence with PT  $\geq 2\%$ )
  - TEAEs by severity by SOC/PT
  - Severe TEAEs by SOC/PT
  - TEAEs related to study medication as assessed by the investigator by SOC/PT
  - Severe TEAEs related to study medication as assessed by the investigator by SOC/PT
- Serious TEAEs by SOC/PT
  - Serious TEAEs by SOC/PT
  - Serious TEAEs by SOC/HLT/PT
  - Serious TEAEs related to study medication as assessed by the investigator by SOC/PT
- TEAEs leading to permanent discontinuation of study treatment by SOC/PT
- Death by SOC/PT
- AESI by AESI category (see [Appendix 10.5](#)) and SOC/PT

The time to first AESIs (TEAE category), serious TEAE, or TEAE leading to permanent treatment discontinuation during the treatment period will be assessed by Kaplan-Meier estimates (K-M plot). In order to detect any safety signals, the hazard ratio (HR) will be provided together with the corresponding 95% confidence interval (CI) for the selected adverse events during the treatment period only. Hazard ratios will be calculated using a Cox model including treatment group and randomization strata as factors. The time is defined as the date of first specific event – the date of first dose + 1. Patients without a specific event will be censored at the end of treatment period.

### **5.8.2. Analysis of Clinical Laboratory Measurements**

Laboratory measurements include clinical chemistry, hematology and urinalysis results, and will be converted to standard international units and US conventional units. Summaries of laboratory variables will include:

- Descriptive statistics of laboratory result and change from baseline by visit
- The number (n) and percentage (%) of patients with abnormal lab value during study whose screening and baseline values are normal (overall and per each lab parameter)
- The number (n) and percentage (%) of patients with treatment-emergent PCSVs overall during the study, during the treatment period and during the follow-up period
- Shift tables based on baseline normal/abnormal and other tabular and graphical methods may be used to present the results for parameters of interest

Listing of all laboratory parameters normal range, abnormal flag and treatment-emergent PCSV by patient and visit will be provided.

### **5.8.3. Analysis of Vital Signs**

Summaries of vital sign variables will include:

- Descriptive statistics of vital sign variable and change from baseline by visit
- The number (n) and percentage (%) of patients with treatment-emergent PCSV
- Shift tables based on baseline normal/abnormal and other tabular and graphical methods may be used to present the results for parameters of interest

Listings of vital sign will be provided with flags indicating the treatment-emergent PCSVs.

### **5.8.4. Analysis of Physical Exams**

The number (n) and percentage (%) of patients with abnormal physical exams will be summarized at baseline, end of treatment period and end of study by treatment group. A summary of treatment-emergent abnormal findings will be provided.

### **5.8.5. Analysis of 12-Lead ECG**

Summaries of 12-lead ECG parameters by treatment group will include:

- Each ECG parameter and change from baseline
- The number (n) and percentage (%) of subjects with PCSV, depending on data
- ECG status (i.e. normal, abnormal) summarized by a shift table

Listings of ECG will be provided with flags indicating PCSVs.

## **5.9. Analysis of Pharmacokinetic Data**

The following analyses will be conducted:

- Descriptive statistics of functional dupilumab serum concentrations at each sampling time by dose
- Graphical presentations of median and mean (+/- SD) functional dupilumab concentration in serum vs nominal time profiles
- Graphical presentations of individual functional dupilumab concentration in serum vs actual sampling time profiles
- Assessment of the impact of anti-drug antibodies on functional dupilumab concentrations in serum

No formal statistical analysis will be performed.

## **5.10. Analysis of Immunogenicity Data**

### **5.10.1. Analysis of ADA Data**

The incidence of ADA variables described in Section 4.7 will be summarized using absolute occurrence (n) and percent of patients (%) with pre-existing immunoreactivity, treatment-emergent, treatment-boostered, persistent ADA responses and titer categories by treatment groups. Listing of all ADA peak titer levels will be provided for ADA positive subjects.

### **5.10.2. Analysis of Neutralizing Antibodies (NAb)**

The absolute occurrence (n) and percent of patients (%) with Nab positive or negative status will be provided by treatment group for patients in the NAb analysis set.

## **5.11. Association of Immunogenicity with Exposure, Safety and Efficacy**

### **5.11.1. Immunogenicity and Exposure**

Associations between key ADA variables and systemic exposure to dupilumab may be explored for the dupilumab treated patients. Plots of dupilumab concentration may be provided for analyzing the potential impact of treatment-emergent, persistent and titer ADA responses (high, moderate or low) on PK.

### 5.11.2. Immunogenicity and Safety and Efficacy

Associations between the ADA response and safety events may be explored.

Associations between the ADA variables and key efficacy endpoints may be explored for the dupilumab treated group. Plots of efficacy variables may be analyzed for potential impact of treatment-emergent ADA on efficacy.

The above mentioned safety and efficacy analyses will be conducted using the following ADA response categories:

- ADA positive patients, that is patients with treatment-emergent or treatment-boosted response,
- ADA negative patients, that is patients with pre-existing immunoreactivity or negative in the ADA assay at all time points
  
- Patients with persistent ADA response,
- NAb positive patients, that is patients who had positive in the NAb assay at any time point analyzed.
- Peak post-baseline titer level in treatment emergent or treatment boosted ADA positive patients:
  - High,
  - Moderate,
  - Low

### 5.12. Analysis of Biomarker Data

Descriptive statistics for the observed values, change from baseline and percent change from baseline values by treatment and visit will be provided for the following biomarker variables:

- TARC
- total serum IgE
- Serum Immunoglobulin profile (IgG/IgM/IgA, IgG subclasses)
- antigen-specific IgE
- Lactate dehydrogenase (LDH)

The Wilcoxon signed-rank test stratified by the baseline disease severity will be used to test if the change or percentage change from baseline value is significantly different from zero. P-value will be reported.

Exploratory analyses for the difference between dupilumab groups and placebo on the change from baseline and percent change from baseline values will be performed using a rank-based ANCOVA model with treatment group and the baseline disease severity as fixed effects, and the relevant baseline values as covariate. Missing value will be imputed by LOCF method for visits between post-baseline to week 16. After week 16, no imputation will be made. P-value for difference from placebo will be provided.

Correlation of baseline TARC (measured value) and IgE (measured value), absolute change or percent change from baseline value of baseline TARC (measured value) and IgE (measured value) with the following clinical endpoints will be explored using the Spearman's rho test. Both Spearman correlation coefficients and p-value will be reported.

- Percent change from baseline to week 16 in EASI score
- Percent change from baseline to week 16 in weekly average of peak daily pruritus NRS
- Change from baseline to week 16 in percent BSA
- Percent change from baseline to week 16 in SCORAD

Correlation of baseline TARC (measured value) and IgE (measured value) with the following clinical endpoints will be explored using the ANOVA model. The model includes the baseline biomarker data as the dependent variable, and treatment group, the responder/nonresponder of below clinical endpoint as the predictor variable. P-value will be provided to indicate significance of the responder/non-responder factor.

- IGA 0-1 at week 16
- EASI-75 at week 16
- improvement (reduction) of weekly average of peak daily pruritus NRS  $\geq 4$  from baseline to week 16

Association of positivity to at least one antigen-specific IgE with the following clinical endpoints will be explored using CMH test stratified by the baseline disease severity. The risk ratio and p-value from the chi squared test will be provided.

- IGA 0-1 at week 16
- EASI-75 at week 16
- improvement (reduction) of weekly average of peak daily pruritus NRS  $\geq 4$  from baseline to week 16

Correlation/association will be implemented on the placebo, dupilumab Q2W, dupilumab Q4W and combined dupilumab (dupilumab Q2W and Q4W) groups, respectively.

All above analyses will be performed on the FAS for:

- All observed data, regardless if rescue treatment is used or data is collected after study drug withdrawal
- All observed data with censoring after rescue treatment use

The proportion of patients for whom biomarker concentrations “normalize” (shift from above normal to within the normal range) at Week 16 will also be evaluated.

The additional analysis will be performed on the following biomarkers at week 16:

- Serum total IgE
- Serum LDH

Serum total IgE and LDH are established clinical assays; the upper limit of normal (ULN) from the central lab reference range will determine the threshold for normal vs. elevated status.

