## 4. SELECTION, WITHDRAWAL, AND REPLACEMENT OF PATIENTS

### 4.1. Number of Patients Planned

Approximately 240 patients are planned to be enrolled into 3 groups (80 per group): dupilumab Q2W treatment groups (200 mg Q2W or 300 mg Q2W), dupilumab Q4W treatment group (300 mg Q4W), or placebo group. The study will be conducted at multiple sites in North America; other regions may be included.

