**6.2.5. Biomarker Procedures**

Thymus and activation-regulated chemokine and total serum IgE are markers of Th2 activity as downstream mediators in the IL-4/IL-13 signaling pathway ([Wirnsberger 2006](#), [Takeda 1997](#)). These analytes will be assessed as measures of Th2 activity and PD effect of dupilumab. The results may be used for modeling dupilumab activity with drug levels in the comparison of dosing regimens. Thymus and activation-regulated chemokine levels have also been closely associated with AD disease activity and severity ([Beck 2014](#)), and will be evaluated as an exploratory marker of efficacy. These markers may also be assessed for their potential value in predicting treatment response.

Lactate dehydrogenase levels have also been shown to correlate with disease severity and activity in patients with AD ([Mukai 1990](#)).

Patients with total serum IgE levels in the normal range may still have antigen-specific IgE in circulation, indicating they are atopic. To further understand atopy in this patient population, region-specific, allergen-specific IgE panels will be performed. These markers may be used to understand PD activity, efficacy, and may be also tested for predictive utility.

Serum samples for measurements of biomarkers (including TARC, total IgE, immunoglobulin profiling, allergen-specific IgE, and LDH [which will be measured as part of the blood chemistry]) to study the PD activity of dupilumab in pediatric AD patients will be collected at time points according to section 6.1.

Additional biomarker serum samples will be collected to study exploratory biomarkers of dupilumab activity and AD.

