#### 9.5.6. Analysis of Biomarker Data

All exploratory biomarker data analyses will be performed on the FAS and no multiplicity adjustment is planned. Analyses of exploratory endpoints will be provided in the SAP.

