## 2.2. Sample Size and Power Considerations

Approximately 240 patients are planned to be randomized to 1 of the following treatment groups:

- Dupilumab Q2W treatment group: 200 mg Q2W patients <60 kg or 300 mg Q2W patients ≥60 kg
- Dupilumab Q4W treatment group: 300 mg Q4W
- Placebo group

It is estimated that with 80 patients per group, at the 2-sided 5% significance level, the study will have:

- 98% power to detect a difference of 28% between dupilumab Q2W treatment and placebo treatment in the percentage of patients who achieve an IGA score 0 to 1 at week 16, assuming that the percentages are 37% and 9% for dupilumab Q2W and placebo, respectively.
- 88% power to detect a difference of 20% between dupilumab Q4W treatment and placebo treatment in the percentage of patients who achieve an IGA score 0 to 1 at week 16, assuming that the percentages are 29% and 9% for dupilumab Q4W and placebo, respectively.
- 99% power to detect a difference of 35% between dupilumab Q2W treatment and placebo treatment in the percentages of patients achieving EASI-75 response at week 16, assuming that the percentages are 48% and 13% for dupilumab Q2W and placebo, respectively.
- 99% power to detect a difference of 32% between dupilumab Q4W treatment and placebo treatment in percentages of patients achieving EASI-75 response at week 16, assuming that the percentages are 45% and 13% for dupilumab Q4W and placebo, respectively.

[figure not shown]
Additional power calculation based on the key secondary endpoint “proportion of patients with improvement (reduction) of Pruritus NRS  $\geq 4$  from baseline to week 16”, with 80 patients per group, the study will provide:

- 97% power at a 0.05 level to detect a difference of 27% in the percentages of patients achieving Pruritus NRS reduction  $\geq 4$  at week 16, assuming that the percentages are 38% and 11% for dupilumab Q2W and placebo, respectively.
- 95% power at a 0.05 level to detect a difference of 25% in the percentages of patients achieving weekly average of daily peak Pruritus NRS reduction  $\geq 4$  at week 16, assuming that the percentages are 36% and 11% for dupilumab Q4W and placebo, respectively.

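### The signed-rank p-value on percentage change in biomarkers is biased toward an increase, because percentage change is not symmetric about zero when nothing has changed (minor, exploratory)

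*SAP*

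**What the plan says.** SAP 5.12 first promises descriptive statistics: observed values, "change from baseline and percent change from baseline values by treatment and visit will be provided for the following biomarker variables". The list is TARC, total IgE, the immunoglobulin profile, antigen-specific IgE and LDH. It then adds a test: "The Wilcoxon signed-rank test stratified by the baseline disease severity will be used", and this "will be used to test if the change or percentage change from baseline value is significantly different from zero". A p-value is to be reported. No log transform is named, and nothing says which of the two scales the reader should rely on.

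The comparison with placebo is a different analysis. It covers both scales and "will be performed using a rank-based ANCOVA model with treatment group and the baseline disease severity as fixed effects".

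Protocol 6.2.5 gives the purpose for TARC and total IgE: "These analytes will be assessed as measures of Th2 activity and PD effect of dupilumab". Protocol 9.5.6 sets the status: "All exploratory biomarker data analyses will be performed on the FAS and no multiplicity adjustment is planned". Neither document gives a within-patient SD for any biomarker, an expected size of fall, or a significance level for these tests.

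**The concern.** The question the SAP puts is whether a marker has moved from baseline. The signed-rank test answers it only if the values would be symmetric about zero when nothing has moved, because its reference distribution is built by flipping signs.

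Percentage change does not have that symmetry. If baseline and follow-up are exchangeable, a doubling is as likely as a halving, but a doubling scores +100% and a halving -50%. The positive values take the larger ranks, and the test can reject for skewness alone. Stratifying by severity does not help, because the skew is present within each stratum.

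At stake is a column of within-arm p-values on the pharmacodynamic markers. In a group where a marker did not move, the column will show a significant rise too often. Where a variable marker fell modestly, the column may show nothing.

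**Working it through.** The plan states no operating characteristic for this test, so there is no figure of its own to reproduce.

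**Inputs**
- Group size: n = 80 (Protocol 4.1).
- Level: "at the 2-sided 5% significance level" in SAP 2.2. That level is stated for the power calculations; applying it to biomarkers is an assumption. Nominal error is 2.5% in each direction.
- Strata: two severity strata (IGA 3 and 4), taken as 40 + 40. The equal split is an assumption.
- Model: log baseline and log follow-up are a patient mean (between-patient SD 1.2) plus independent errors, so the log ratio L = ln(post/baseline) is normal with SD s and centred at 0 when nothing changes. Both s (range 0.1 to 1.0) and the 1.2 are assumptions. The 1.2 affects only absolute change.

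**Formulae**
- Percentage change = 100 × (exp(L) − 1).
- Test: Z = Σ(signed ranks) / √Σ(ranks²), ranks taken within stratum and both sums over the two strata. Reject if |Z| > 1.96.

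**Why the sign tilts.** Take one doubling and one halving. On percentage change the values are +100 and −50, the ranks of the absolute values are 2 and 1, and the signed sum is 2 − 1 = +1. On the log scale the values are +0.693 and −0.693, the ranks tie at 1.5, and the sum is 1.5 − 1.5 = 0.

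**No true change, n = 80: chance of a significant increase on percentage change (nominal 2.5%)**

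| s | 0.1 | 0.2 | 0.3 | 0.5 | 0.7 | 1.0 |
|---|---|---|---|---|---|---|
| False increase | 4% | 6% | 9% | 15% | 23% | 36% |

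False decreases are 1.6% at s = 0.1, 1.0% at s = 0.2 and below 1% from s = 0.3. Absolute change and the log ratio stay near 2.5% each way at every s, because exchangeable pairs give symmetric differences. With n = 40, to allow for missing samples, the false-increase rate is 4.3%, 10.7% and 19.0% at s = 0.2, 0.6 and 1.0.

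**Where the test on percentage change is centred.** With no change, the pseudomedian of percentage change is +3.9% at s = 0.4, +8.4% at 0.6 and +22.1% at 1.0. A true fall multiplies every ratio by the same factor, so the statistic is centred near zero when the median ratio is 1/(1 + pseudomedian):
- s = 0.4: 1/1.039 = 0.962, a fall of about 4%
- s = 0.6: 1/1.084 = 0.923, about 8%
- s = 1.0: 1/1.221 = 0.819, about 18%

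A true median fall of that size looks like no change.

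**True 20% median fall, n = 80: power**

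| s | Percentage change | Absolute change | Log ratio |
|---|---|---|---|
| 0.5 | 79% | 92% | 97% |
| 0.7 | 30% | 66% | 78% |
| 1.0 | 5% | 40% | 48% |

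At s of 0.3 or less a 20% fall is detected essentially always on all three scales. A 50% fall is detected at least 97% of the time on any scale up to s = 1.0. Repeated runs agree within about two percentage points.

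**The case against.** The strongest reply is that little depends on this p-value. The biomarker analyses are exploratory and outside the testing hierarchy in SAP 5.7.2. Treatment effect is judged against placebo by the rank-based ANCOVA, which does not test against zero. A within-arm p-value is weak evidence of drug effect on any scale, because it also absorbs regression to the mean and time trends. All of this stands, and it is why the point is minor.

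Second, the same sentence also allows absolute change. That test holds its level and recovers most of the lost power. This stands too, but the SAP gives two p-values for one question and no rule for choosing between them.

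Third, the size rests on an SD that the documents do not give, and one range is applied to very different markers. That also stands: at s = 0.1 to 0.2 total rejection is about 5.5% (3.9 + 1.6) to 6.7% (5.7 + 1.0), close to nominal.

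A reader might go further and infer that unchanged arms will be declared to have risen, or that dupilumab's real effects will be missed. The documents support neither. The first is a raised error rate, not an outcome. The second would need an expected fall, which is not stated, and large falls are found on every scale. Nor should the problem be sized on the combined dupilumab group: SAP 5.12 uses that group for correlation and association only.

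Finally, the test sentence does not itself say by arm and visit. I read it so because it follows the by-treatment summaries and SAP 5 summarises all data by three groups.

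**Conclusion.** The point holds as a minor defect. The signed-rank p-value on percentage change does not test what SAP 5.12 says it tests. With no true change its false-increase rate runs from about 4-6% (s = 0.1-0.2) to 36% (s = 1.0). The top of that range is about 14 times nominal (36/2.5 = 14.4). It can also miss modest falls in variable markers.

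The size rests on assumed SDs, roughly log-normal exchangeable pairs, 80 patients split equally by severity, and a within-arm reading at two-sided 5%. The direction of the bias needs only that doublings and halvings be equally likely when nothing has changed. No efficacy conclusion or alpha depends on this p-value.

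**What to change.** In SAP 5.12:
- Run the stratified signed-rank test on ln(post/baseline), and report the back-transformed percent change with that p-value.
- Keep raw percentage change as a descriptive summary with no signed-rank p-value. If the test on absolute change is retained, state that the log ratio is the scale to rely on.
- State that the LLOQ/2 rule of SAP 6.2 is extended to the biomarkers. As written it covers laboratory safety variables. LDH is in that panel, but TARC, IgE and the immunoglobulins are listed separately in SAP 4.8.

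The cost is a short SAP edit and a log transform in the program, with no new data. The downside is one fewer p-value column. Two limits remain. Symmetry of the log ratio is still an assumption, though a milder one. For a marker with many values below LLOQ, substitution produces ties and zero log ratios, which were not simulated here.

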### 1.2.2. Rationale for Dose Selection

The dose justification for adolescent pediatric patients aged  $\geq 12$  to  $< 18$  years is based on the observed efficacy and safety in the dose ranging study in adult AD patients (R668-AD-1021), the observed efficacy and safety in the phase 3 monotherapy studies in adult AD patients (R668-AD-1334 and R668-AD-1416), the observed PK data, efficacy, and safety results in a pediatric AD study of patients  $\geq 6$  to  $< 18$  years old (R668-AD-1412), and the modeling performed on the PK data obtained from this pediatric study.

The adult dose-ranging study evaluated dupilumab dose regimens of 300 mg QW, 300 mg Q2W, 300 mg Q4W, 200 mg Q2W, and 100 mg Q4W versus placebo, administered for 16 weeks. All 5 dose regimens were efficacious. Efficacy data suggested a dose-response pattern for most efficacy outcome measures, including EASI, IGA, and pruritus scores, for which the corresponding endpoints at week 16 were generally aligned in the same rank order as the total monthly dose and the mean concentrations of functional dupilumab at week 16. Thus, the 300 mg QW regimen was consistently the most efficacious dose regimen in this study across multiple endpoints, followed closely by the 300 mg Q2W dose regimen. Differences in the efficacy and safety outcomes between the 300 mg QW and 300 mg Q2W were relatively small. The 200 mg Q2W and 300 mg Q4W doses also showed good efficacy responses but were numerically inferior to the 300 mg Q2W and 300 mg QW regimens for the majority of efficacy endpoints. The efficacy of the 100 mg Q4W regimen (100 mg total monthly dose) appeared to be sub-optimal.

The dose regimens of 300 mg QW and 300 mg Q2W provided the most consistent clinical benefit and both had an acceptable safety profile. However, 300 mg QW and 300 mg Q2W dosing did not show clear differentiation in EASI and IGA changes from baseline in study R668-AD-1021. More recently, the lack of clear differentiation between 300 mg QW and 300 mg Q2W dosing was further confirmed in 2 pivotal studies (R668-AD-1334 and R668-AD-1416) in adults based on EASI and IGA data. As PK modeling for dupilumab has shown weight to be the most important covariate influencing exposure, the use of the 300 mg QW regimen in adolescents with low body weight may lead to systemic exposure greater than

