### 9.1. Statistical Hypothesis

The following null hypothesis and alternative will be tested for each dupilumab treatment group:

H0: No treatment difference between dupilumab and placebo

H1: There is a treatment difference between dupilumab and placebo

Baseline weight group (<60 kg and  $\geq 60$ kg) and disease severity (moderate [IGA=3] vs. severe [IGA=4] AD) will be the 2 stratification factors for patient randomization and will be accounted for in the statistical modeling for efficacy.

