#### 5.7.1. Analysis of Primary Efficacy Variable

The Cochran-Mantel-Haenszel (CMH) test adjusted by randomization strata (disease severity (IGA=3 or 4), weight group (<60 kg or ≥60kg)) will be used for the analysis of percentage of patients with IGA 0 or 1 at week 16 or percentage of patients with EASI-75 at week 16.

All efficacy data, regardless of the patient being on the study treatment or discontinues the study treatment but remains in the study, will be used for analysis. Specifically, if a patient stays in the study until the end of the study planned placebo-controlled treatment period, all efficacy data collected up to the study planned end of treatment visit will be included in the primary analysis, regardless if the patient is on treatment or not.

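### The dupilumab-versus-placebo biomarker ANCOVA in SAP 5.12 omits weight group, one of the two randomization strata, without giving a reason

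*SAP*

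**What the plan says.** Protocol 9.1 names baseline weight group and disease severity and says that they "will be the 2 stratification factors for patient randomization and will be accounted for in the statistical modeling for efficacy". SAP 2.1 repeats the two strata, with about 120 patients planned in each weight stratum and 1:1:1 allocation. The primary CMH test in SAP 5.7.1 is "adjusted by randomization strata (disease severity (IGA=3 or 4), weight group", so it uses both.

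For the biomarkers (TARC, total IgE, immunoglobulins, antigen-specific IgE, LDH), SAP 5.12 compares dupilumab with placebo by a "rank-based ANCOVA model with treatment group and the baseline disease severity as fixed effects, and the relevant baseline values as covariate". The model therefore holds treatment, severity and the baseline biomarker value. Weight group appears nowhere in SAP 5.12, and SAP 1.2.3, which lists changes from the protocol's statistical section, does not mention it.

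On status, Protocol 9.5.6 says: "All exploratory biomarker data analyses will be performed on the FAS and no multiplicity adjustment is planned".

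**The concern.** A model for a randomized comparison normally carries the factors that the randomization was stratified on. Stratifying removes chance imbalance in weight between arms. If the model leaves weight out, whatever variance weight explains stays in the residual, and the reported standard error is larger than the design warrants. The test is then conservative and loses some power.

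There is a reason to think that weight could matter. Protocol 1.2.2 states that "PK modeling for dupilumab has shown weight to be the most important covariate influencing exposure", and the Q4W arm receives the same dose whatever the weight. The biomarkers are pharmacodynamic measures, so a relation between weight and biomarker change is plausible, though no document shows one.

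Exploratory status does not by itself explain the omission. Other analyses outside the hierarchy keep the randomization strata: the subgroup interaction models (SAP 5.7.3), the other efficacy variables (SAP 5.7.4, by reference to the primary methods) and the Cox models for selected adverse events (SAP 5.8.1). At stake is some precision in exploratory p-values.

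**Working it through.** **Plan's own figure.** There is none to reproduce. The documents give no power, standard deviation or weight effect for any biomarker. The sample-size statement ("It is estimated that with 80 patients per group, at the 2-sided 5% significance level") concerns binary efficacy endpoints; only the 80 per group is used below.

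**Step 1: terms side by side.**

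| | Severity | Weight group | Baseline value |
|---|---|---|---|
| Randomization (Protocol 9.1, SAP 2.1) | yes | yes | – |
| Primary CMH test (SAP 5.7.1) | yes | yes | – |
| Biomarker rank ANCOVA (SAP 5.12) | yes | no | yes |

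**Step 2: direction.** Weight is balanced between arms by the stratified randomization. Omitting it does not shift the expected treatment difference; it only inflates the residual variance.

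**Step 3: size.** Let R² be the share of the ANCOVA's residual variance that weight group explains. Adding the term multiplies the standard error by √(1 − R²). The same shortening would need 1/(1 − R²) − 1 more patients. R² is assumed, and on ranks the formula is approximate.

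| Assumed R² | √(1 − R²) | SE shorter by | Equivalent extra patients |
|---|---|---|---|
| 0.02 | 0.990 | 1.0% | 2.0% |
| 0.05 | 0.975 | 2.5% | 5.3% |
| 0.10 | 0.949 | 5.1% | 11.1% |

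**Step 4: simulation of the test.** Rank ANCOVA, 80 versus 80, two-sided 0.05, 5,000 trials per setting. All effects are assumed, in residual SD units: treatment 0 or 0.45, severity 0.3, weight group g; slope on the baseline value 0.4; severity and weight both split 50:50 and balanced across arms. With a 50:50 split the weight term has variance g²/4, so R² = (g²/4)/(1 + g²/4); for g = 1.0 this is 0.25/1.25 = 20%.

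| g | R² | Type I error without / with weight | Power without / with weight |
|---|---|---|---|
| 0 | 0% | 5.4% / 5.4% | 78.7% / 78.6% |
| 0.3 | 2.2% | 5.2% / 5.3% | 77.5% / 78.3% |
| 0.5 | 5.9% | 4.4% / 5.0% | 75.6% / 77.3% |
| 0.8 | 13.8% | 3.7% / 5.1% | 73.0% / 77.4% |
| 1.0 | 20.0% | 3.3% / 5.2% | 70.9% / 77.6% |

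The Monte Carlo standard error is about 0.3 points for type I error and 0.6 points for power. R² = 0.10 corresponds to g = 2√(0.10/0.90) = 0.67, between the 0.5 and 0.8 rows. Over the assumed 2% to 10% range the power lost therefore runs from about 1 point to less than 4.4 points (77.4 − 73.0). With no weight effect the two models perform alike.

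**The case against.** The strongest reply is that no rule is broken. The commitment in Protocol 9.1 is worded for efficacy models, biomarkers are not efficacy endpoints, and Protocol 9.5.6 leaves these analyses to the SAP. Severity is a reasoned choice, since Protocol 6.2.5 links TARC and LDH to disease severity, and the ANCOVA also carries the baseline biomarker value. Protocol 1.2.2 ties weight to drug exposure, not to the biomarkers. Placebo patients have no exposure, and the tiered Q2W dose is expected to give similar mean exposure in both weight groups, which leaves mainly the Q4W arm.

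All of this stands. It makes the omission an unexplained departure from the stratified design rather than a contradiction, and it makes a small weight effect more likely than a large one. It gives no reason to leave the stratum out.

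A reader might also infer more than the documents support:

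- **That the other severity-stratified tests share the fault.** The association of antigen-specific IgE positivity with clinical response "will be explored using CMH test stratified by the baseline disease severity", but it is run within placebo, Q2W, Q4W and combined dupilumab, and positivity is not randomized. The argument about standard errors under stratified randomization does not apply. Nor does it apply to the test of change from zero ("The Wilcoxon signed-rank test stratified by the baseline disease severity will be used"), which is not a comparison between arms.
- **That the comparison is meant to support the weight-tiered dose.** No section says so. Protocol 1.2.2 rests that dose on adult efficacy and safety, exposure matching and injection volume. Protocol 6.2.5 mentions possible modelling of biomarkers against drug levels, which is a different analysis. A main-effect weight term would not show whether the biomarker effect differs by weight in any case.
- **That every efficacy model adjusts for both strata.** SAP 5.7.2 twice names age group in place of weight group, although its list for the imputation model names weight group.

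**Conclusion.** The point holds for the rank-based ANCOVA against placebo in SAP 5.12, and only there. The model leaves out one of two randomization strata without a stated reason. The treatment comparison is not biased, and false positives are not inflated. The consequence is at most mild conservatism: standard errors about 1% to 5% longer than needed, if weight group explains 2% to 10% of residual variance. That range is an assumption; the true share could be zero, in which case nothing is lost either way. The larger power loss in the last row of the simulation (77.6% to 70.9%) needs a weight effect of 1.0 residual SD, or R² of 20%, twice the top of the range.

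No primary, key secondary or other hierarchy endpoint is affected. This is a worthwhile refinement of an exploratory analysis, of low priority.

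**What to change.** In SAP 5.12, add weight group (<60 kg, ≥60 kg) as a fixed effect in the rank-based ANCOVA, beside treatment group, baseline disease severity and the baseline biomarker value, so that the model matches the randomization strata. If the omission was deliberate, one sentence giving the reason would do instead.

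The cost is one SAP sentence before database lock and one degree of freedom in the model. No new data are needed: weight group is recorded for randomization, and SAP 5.7.2 does not expect the strata to be missing. The within-group tests in SAP 5.12 need no change on this ground.
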